1 INTRODUCTION

1.1 *Disease Background*

Huntington disease (HD) is a fatal neurodegenerative autosomal dominant disorder characterized by progressive motor, cognitive, and behavioral symptoms that cause profound disability. The adult onset form of HD typically manifests between 35 and 40 years of age. Progression of the disease is slow and inexorable, with death ensuing approximately 10 to 20 years after onset of the first motor symptoms. The worldwide prevalence of HD is estimated to be 5-10 cases per 100,000 persons.

Histopathologically, HD is characterized by progressive loss of medium spiny neurons in the striatum and to a lesser extent of pyramidal neurons in the cortex. The disease is due to a mutation in the polyglutamine repeat sequence in the *huntingtin* gene located on Chromosome 4.

The most commonly recognized motor sign of HD is the involuntary movement chorea, which can affect all muscle groups. Chorea has the potential to interfere with daily functioning. In its early stages, chorea can contribute to impaired speaking, writing, and Activities of Daily Living (ADLs) such as feeding, dressing and bathing. In its later stages, chorea can cause gait instability and poor postural control, with an increased risk of injury from falling or flailing into objects.

Both preclinical studies in transgenic mice and clinical experience in patients with a genetic predisposition to HD implicate a relative excess of dopamine in the pathogenesis of these involuntary movements. These observations led to the development of tetrabenazine, which depletes presynaptic dopamine, as a treatment for chorea associated with Huntington disease.

1.2 *Tetrabenazine*

Tetrabenazine is approved in the United States (US), Canada and several European Union (EU) countries as a therapy for the treatment of chorea associated with Huntington disease (HD). Tetrabenazine is rapidly and extensively converted in the liver by carbonyl reductase to alpha-dihydro-tetrabenazine (α -HTBZ) and beta-dihydro-tetrabenazine (β -HTBZ). These metabolites are potent and selective inhibitors of vesicular monoamine transporter (VMAT)-2, resulting in reduced storage and release of presynaptic dopamine, and are responsible for mediating the *in vivo* efficacy of orally administered tetrabenazine.

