Subjects Switching from Tetrabenazine (Switch): Subjects who are currently receiving an FDA approved dose of tetrabenazine (TBZ) that is providing a therapeutic benefit for chorea control associated with HD will be eligible to participate in the study. Subjects in this cohort will undergo a full screening evaluation within 30 days of the Baseline assessment prior to switching to SD-809 ER. See Schedule of Events A. These subjects will be converted from their TBZ regimen to an SD-809 ER regimen that is predicted to provide comparable exposure to total ($\alpha+\beta$)-dihydro-tetrabenazine (α - and β -HTBZ). Subjects will continue taking their TBZ regimen through midnight of Day 0 and then directly switch to their assigned SD-809 ER regimen the next morning. The dose of SD-809 ER may be adjusted weekly (upward or downward) in increments of 6 mg per day (6 mg/day or 12 mg/day after a total daily dose of 48 mg is reached) to identify a dose level that adequately controls chorea, the subject experiences a protocol defined "clinically significant" adverse event (defined as related to study medication and either a) moderate or severe in intensity or b) meets the criteria for a Serious Adverse Event [SAE])¹; or the maximal allowable dose is reached. If a subject experiences a "clinically significant" AE attributable to SD-809 ER, the investigator will determine if a dose reduction or suspension is necessary. The investigator, in consultation with the subject and caregiver, will determine when an adequate level of chorea control has been achieved. Subjects will have a clinic visit at Week 1 and a telephone contact at Week 2, in order to evaluate safety and establish an optimal dose. Although subjects will enter the Long term treatment period after Week 2, dose adjustment (upward or downward) may continue through Week 4 to optimize dose level. Additional dose adjustments may be made after Week 4 if clinically indicated.

Subjects Enrolled from the SD-809-C-15 Study (Rollover): Subjects who have successfully completed Study SD-809-C-15 may be eligible to rollover directly into this study after they complete a one week washout and the Week 13 evaluation of Study SD-809-C-15. To reduce subject burden, after obtaining capacity assessment (if applicable)/informed consent/assent and

¹ See Section 7 for evaluation of AEs regarding severity, relationship to study drug and definition of SAE.

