Subjects Enrolled from the SD-809-C-15 Study (Rollover): Subjects who have successfully completed Study SD-809-C-15 may be eligible to rollover directly into this study after they complete a 1-week washout period and the Week 13 evaluation of Study SD-809-C-15. To reduce subject burden, the Week 13 evaluation will provide some Baseline data for the present study. Additional evaluations required as part of the SD-809-C-16 study may be completed on the same day as the Week 13 visit of the SD-809-C-15 study after SD-809-C-16 informed consent/assent is obtained. If subjects are unable to enroll at the Week 13 visit they will have up to 3 weeks to complete the additional evaluations for Baseline or the subject will not be eligible to enroll in this study. In addition, following informed consent/assent, prior data from Study SD-809-C-15 can be used in this study as part of the subject’s medical history information.

As Rollover subjects will have discontinued study drug (SD-809 or placebo) for at least 1 week at completion of the SD-809-C-15 study, they will undergo titration on SD-809. During titration, the Investigator, in consultation with the subject and caregiver, will determine when an adequate level of chorea control has been achieved. The dose of SD-809 may be adjusted (upward or downward), in increments of 6 mg per day (each week) (6 mg/day or up to 12 mg/day after a total daily dose of 48 mg is reached), until there is adequate control of chorea, the subject experiences a protocol defined “clinically significant” adverse event, as outlined above, or the maximal allowable dose is reached. If a subject experiences a “clinically significant” AE attributable to SD-809, the Investigator will determine if a dose reduction or suspension is necessary. Although subjects will enter the long-term treatment period after Week 2, titration may occur through Week 8 to optimize dose level. Additional dose adjustments may be made after Week 8 if clinically indicated.

Long-Term Treatment Period: During long-term treatment, further dose adjustments of SD-809 may be made, if necessary, but not more often than weekly. Dose adjustments should be based on all available information including the subject's and caregiver's reports of adverse events and chorea control, information from rating scales, and all safety evaluations. The Long-Term Treatment Period will continue until SD-809 becomes commercially available in the U.S.

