8.8 Time Periods for Analyses

Some analyses will be performed by time period. For these analyses, the following definitions will be used:

- Screening Period (Switch subjects only) - from informed consent until the first dose of study drug
- Dose-Adjustment Period (Switch subjects only) – Baseline through Week 4
- Extended Dose-Adjustment Period (Switch subjects only) – Baseline through Week 8
- Titration Period (Rollover subjects only) – Baseline through Week 8
- Stable-Dose Period - from Week 8 through the last dose of study drug
- Entire Treatment Period - Baseline through last dose of study drug
- Follow-up Period - from the last dose of study drug through the end of the study

Subjects who withdraw from the study during the Titration Period or the Extended Dose-Adjustment Period will not have a Stable-Dose Period. For the analyses of adverse events, to be conservative, all follow-up adverse events will be counted as events that occurred during the last available treatment period prior to the Follow-up period.

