8.9 Analysis Visit Windows

For efficacy and safety by-visit analyses, data collected at post baseline scheduled visits will be included using their nominal visit. Data collected at early termination, end of treatment, and unscheduled visits will be assigned to a visit window as described below. All scheduled visits will be assigned a target study day; for the determination of target days, weeks will be assumed to have 7 days. Thus, Week 4 would have a target day of $4 \times 7 = 28$ days. For each visit, a visit window will be assigned so that anything from the midpoint to the prior target day to the midpoint to the following target day will be assigned to that visit window as shown in Table 3 below. The following rules concerning visit windows and selecting records for analysis will be used:

1. Scheduled visit has precedence.

2. If there are multiple records of the same scheduled visit, the record closest to the target day will be used for analysis. If two records are equidistant, then the earlier one will be used.
3. For a given visit, if there is no data from a scheduled visit, data from an unscheduled visit that occurs in the visit window will be used for analysis.

Table 3: Analysis Visit Window

| Visit | Target Day | Visit Window |
|-----------------------------|------------|--------------|
| Screening | -5 | (--, -5) |
| Screening Telephone Contact | -2 | (-4, -2) |
| Baseline | -1 | (-1, -1) |
| Week 1 | 7 | (1,10) |
| Week 2 | 14 | (11-17) |
| Week 3 | 21 | (18, 24) |
| Week 4 | 28 | (25, 31) |
| Week 5 | 35 | (32, 38) |
| Week 7 | 49 | (39, 52) |
| Week 8 | 56 | (53, 80) |
| Week 15 | 105 | (81, 150) |
| Week 28 | 196 | (151, 241) |
| Week 41 | 287 | (242, 332) |
| Week 54 | 378 | (333, 423) |
| Week 67 | 469 | (424, 514) |
| Week 80 | 560 | (515, 605) |
| Week 93 | 651 | (606, 697) |
| Week 106 | 742 | (698, 787) |
| Week 119 | 833 | (788, 879) |
| Week 132 | 924 | (880, 970) |
| Week 145 | 1015 | (971, 1060) |
| Week 158 | 1106 | (1061, 1152) |
| Week 171 | 1197 | (1153, --) |

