9.9.1 Adverse Events

Adverse events will be coded using version 16.1 of the Medical Dictionary for Regulatory Activities (MedDRA); the MedDRA version will be noted in the CSR. Treatment-emergent AEs (TEAEs) are events that 1) begin after treatment with study drug in the current study and that are not present at baseline or 2) if present at baseline, have worsened in severity. For AEs with missing start dates, the AE will be considered treatment-emergent unless there is additional information indicating that the AE started prior to the first treatment. All analyses of TEAEs will be performed separately for TEAEs that occurred during the titration period (for Rollover subjects only), during the dose-adjustment period (for Switch subjects only), during the extended dose-adjustment period (for Switch subjects only), during the stable dose period, and during the entire treatment period. To be conservative, all adverse events that occurred during the follow-up period will be counted as events that occurred during the last available treatment period. In order to be included in the analysis for a given time period, a subjects must have at least one visit during the time period.

For the Switch cohort, an overview of AEs occurring during the Screening period will present the number and percentage of subjects in the following categories:

- Any AEs
- Any serious AEs (SAEs)
- Any severe AEs
- Any AE(s) leading to death

An overview of TEAEs will present the number and percentage of subjects in the following categories:

- Any TEAEs
- Any serious TEAEs

-
- Any severe TEAEs
 - Any treatment-related TEAEs
 - Any TEAEs resulting in dose reduction
 - Any TEAEs resulting in dose suspension
 - Any TEAEs resulting in withdrawal from the study
 - Any treatment-related TEAEs resulting in withdrawal from the study
 - Any TEAEs resulting in dose reduction, dose suspension, or withdrawal from the study
 - Any TEAE(s) leading to death

TEAEs, serious TEAEs, TEAEs that led to dose reduction, TEAEs that led to dose suspension, TEAEs that led to withdrawal from the study, TEAEs that occurred in at least 4% of Rollover or Switch cohort subjects in the Safety Population across all time periods, will be summarized at the subject level by MedDRA system organ class (SOC) and preferred term using frequencies and percentages.

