Exposure adjusted incidence rates (number of patients with an event per person-year) will also be presented for the above TEAE overview categories, all preferred terms, and selected AEs of interest by patient cohort and study (First Active in C15, First Placebo in C15, Rollover in C16, and Switch in C16). AEs of agitation, somnolence, insomnia, anxiety and fall will be defined as events with matched preferred terms. In addition, AEs with selected preferred terms will be combined into the AEs of interest as follows:

- Akathisia and Restlessness: Akathisia, Hyperkinesia, Psychomotor hyperactivity, Restlessness, Agitation
- Dysphagia: Aphagia, Dysphagia
- Parkinsonism: Akinesia, Bradykinesia, Cogwheel rigidity, Freezing phenomenon, Hypertonia, Masked facies, Muscle rigidity, On and off phenomenon', Parkinsonian crisis, Parkinsonian gait, Parkinsonian rest tremor, Parkinsonism, Parkinson's disease, Resting tremor
- Suicidality: Completed suicide, Depression suicidal, Intentional overdose, Intentional self-injury, Poisoning deliberate, Self-injurious ideation, Suicidal behavior, Suicidal ideation, Suicide attempt.
- Depression: all preferred terms containing “depression”

Incidence rate will be calculated as:

Number of patients with given event/ Person-years for the event

Person-years for a selected event are defined as the sum of exposure days across all subjects divided by 365.25. Subjects with an event of the given type contribute days from the date of their first treatment dose until the date of the first event of the given type. Subjects without an event of the given type contribute days from date of their first treatment dose until their treatment end date. Events that occurred after the last dose date of each study period were not included.

TEAEs and treatment-related TEAEs, categorized by system organ class, preferred term, and maximum severity (mild, moderate, or severe), will be summarized by study period using counts and percentages. In addition, TEAEs, categorized by system organ class, preferred term, and relationship to study drug (unrelated, related), will be summarized by study period using counts and percentages. TEAEs that are classified as possibly, probably, or definitely related to study drug on the AE eCRF, or for which the relationship to study drug is missing, will be considered treatment related. Unrelated AEs include those classified as unrelated or unlikely related on the AE eCRF.

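### SAP 9.9.1 shows person-year AE rates from about 12 weeks of C-15 beside rates from open-ended C-16 treatment, with no common follow-up window

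*SAP*

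**What the plan says.** SAP Section 9.9.1 (Adverse Events) plans person-year rates for the TEAE overview categories, every preferred term and the selected AEs of interest, "by patient cohort and study (First Active in C15, First Placebo in C15, Rollover in C16, and Switch in C16"). The numerator is the number of subjects with the event. The denominator is person-time from first dose to the first such event, and "Subjects without an event of the given type contribute days from date of their first treatment dose until their treatment end date". Events after the last dose of each study period are left out. No shared cut-off, no rates by time since first dose and no statement about a constant hazard appear.

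Follow-up differs greatly between the studies:

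- **C-15.** Protocol Section 3.1 has Rollover subjects enter after they "complete a one week washout and the Week 13 evaluation of Study SD-809-C-15". That implies about 12 weeks on treatment; the documents do not state the length outright.
- **C-16.** SAP Section 4 says "The Long-Term Treatment Period will continue until SD-809 becomes commercially available in the U.S". Table 3 in SAP Section 8.9 runs to Week 171 (target day 1197), with the last window open above.

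The same SAP section also says: "All analyses of TEAEs will be performed separately for TEAEs that occurred during the titration period (for Rollover subjects only"), and goes on to the other periods. SAP Section 8.8 defines these as baseline to Week 4, baseline to Week 8, "Stable-Dose Period - from Week 8 through the last dose of study drug", and the entire treatment period.

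**The concern.** Subjects with a first event divided by person-time to that event is an average hazard over the follow-up observed. Averages over 12 weeks and over one to three years estimate the same quantity only if the hazard does not change with time.

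The documents give reasons to doubt that, in both directions. Rollover subjects restart at the lowest dose and titrate for up to 8 weeks, and Switch subjects convert overnight and then adjust, so tolerability events may cluster early. Protocol Section 1.1 says of Huntington disease: "Progression of the disease is slow and inexorable". Events such as falls, dysphagia or depression may therefore become more frequent later.

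The display includes a C-15 placebo column, which invites the reader to judge long-term AE burden against it. A difference between columns could then reflect length of follow-up rather than risk. SAP Section 2 says the planned analyses will go into regulatory submissions or manuscripts.

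**Working it through.** The plan states no event rate, so there is no figure of its own to reproduce. The check applies the SAP's estimator to one hazard shared by both studies.

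**Inputs from the documents.** Estimator: SAP 9.9.1. C-15 treatment: 12 weeks (inferred). C-16 treatment: open-ended. Planned numbers: about 80 Rollover and 36 Switch subjects (Protocol Section 3).

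**Assumptions.** 10% risk in the first 8 weeks; later hazard equal to r times the early hazard; C-16 exposure of 1, 2 or 3 years.

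**Formula.** Early hazard h1 = −ln(0.90)/(8 weeks) = 0.687 per person-year (PY). Expected rate over follow-up T = P(event by T) / E[min(time to event, T)].

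**Example, r = 0.25.**

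- At 12 weeks: cumulative hazard 0.1054 + 0.0132 = 0.1185; risk 0.1118; mean person-time 0.2141 years; rate 0.522/PY.
- At 2 years: cumulative hazard 0.1054 + 0.3173 = 0.4226; risk 0.3447; mean person-time 1.570 years; rate 0.220/PY.
- Ratio: 2.38, at identical risk.

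| r | C-15, 12 weeks (/PY) | C-16, 1 / 2 / 3 years (/PY) | C-15 ÷ C-16 |
|---|---|---|---|
| 1 | 0.687 | 0.687 / 0.687 / 0.687 | 1.00 / 1.00 / 1.00 |
| 1/2 | 0.578 | 0.406 / 0.380 / 0.372 | 1.42 / 1.52 / 1.55 |
| 1/3 | 0.541 | 0.309 / 0.273 / 0.262 | 1.75 / 1.98 / 2.06 |
| 1/4 | 0.522 | 0.260 / 0.220 / 0.206 | 2.01 / 2.38 / 2.53 |
| 1/10 | 0.489 | 0.170 / 0.121 / 0.105 | 2.87 / 4.02 / 4.65 |

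Varying the 8-week risk from 5% to 30% changes little: 1.4–1.6 for r = 1/2, 1.9–2.6 for r = 1/4, 2.7–4.7 for r = 1/10.

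**Rising hazard.** If the hazard doubles after year 1, the 2- and 3-year C-16 rates are 0.876 and 0.908 against 0.687 for C-15. C-16 looks 1.27 and 1.32 times worse.

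**Second shape.** With a 10% 12-week risk and the change placed at Week 12, the C-16 ÷ C-15 ratio at 54 / 106 / 171 weeks is 0.62 / 0.57 / 0.55 (hazard halves), 0.43 / 0.35 / 0.31 (falls to a quarter) and 1.70 / 1.78 / 1.81 (doubles). Constant individual hazards that merely differ between subjects (gamma frailty, variance 1) give 0.87 / 0.76 / 0.68. A simulation of 2,000,000 subjects matched the quarter-hazard case (0.460 and 0.159 against 0.458 and 0.159 at 12 and 106 weeks).

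**Illustration against placebo.** Suppose the drug doubles the hazard throughout and both hazards fall to 25% after Week 8. C-16 drug over 2 years shows 0.220/PY; C-15 placebo shows 0.259/PY. The drug looks slightly better, although the 2-year risks are 34.5% and 19.0%. Capped at 12 weeks, the rates are 0.522 and 0.259, a ratio of 2.0.

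**Do the existing periods help?** An 8-week C-16 rate against a 12-week C-15 rate, at identical risk, gives 1.19 (r = 1/2), 1.32 (1/4), 1.41 (1/10) and 1.47 (r = 0). If the hazard doubles after Week 8 it gives 0.76. The gap is smaller but not removed.

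**The case against.** The strongest reply is that the SAP already splits all TEAE analyses by period, and that the exclusion of events after each study period's last dose could mean the rates are split too. On that reading a Titration Period rate exists and the mismatch is 8 against 12 weeks. The reading is possible, but it does not settle the matter. The entire-treatment rate is still shown, no period is 12 weeks long, and no matching cut of C-15 is defined. The person-time formula also starts at first dose, so it does not fit a period that begins at Week 8.

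The display is descriptive: SAP Section 8.1 rules out formal testing, and no ratio or interval between the groups is planned. This is therefore a risk of misreading and not an error-rate problem. Counts by period elsewhere in Section 9.9.1 will show early clustering within C-16, which helps, but they supply no C-15 counterpart.

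The hazard shapes are assumed. The placebo illustration is the most exposed: it needs the placebo hazard to fall as well, which drug titration does not explain. Differences in susceptibility lower first-event rates on any treatment, but a fall to 25% on placebo is a possible case and not an expected one.

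Two further limits stand. The C-15 length is inferred. A common window also leaves selection untouched: Rollover subjects completed C-15 without ongoing serious or severe events, some had already taken the drug, and Switch subjects were stable on tetrabenazine.

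**Conclusion.** The concern holds. As written, the four columns cover very different lengths of follow-up, and they can be compared only under a constant hazard that the SAP neither states nor checks. At identical risk the distortion is nil for a constant hazard, about 1.4- to 4.7-fold in favour of C-16 under the declining hazards examined, and about 1.3-fold against it if the hazard doubles after year 1. These sizes depend on assumed event timing and exposure; that the bias can run either way does not. The SAP should be changed, although no formal inference is affected.

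**What to change.** In SAP Section 9.9.1, for the cross-study display:

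1. Add rates with events and person-time truncated at 12 weeks from first dose in all four groups, or at the actual C-15 treatment length if that differs.
2. Give C-16 rates after Week 12 as a separate interval.
3. Keep the overall rates, with a note that follow-up differs between studies and that comparing them assumes a constant hazard.

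Under identical risk the truncated C-16 ÷ C-15 ratio is 1.00 in every scenario above. The note should also say that differences in how the cohorts were selected remain.

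The cost is SAP wording and a little programming from AE and dosing dates already held; no new data are needed. The price is precision. With 80 Rollover and 36 Switch subjects, the cap leaves 80 × 0.2141 = 17.1 and 36 × 0.2141 = 7.7 person-years. In the r = 0.25 case that means 80 × 0.1118 = 8.9 and 36 × 0.1118 = 4.0 expected events. Exact Poisson 95% intervals for 9 and 4 events are 0.24–1.00 and 0.14–1.33/PY. Rare preferred terms will have few or no events in the window, which is a further reason to keep the overall rates alongside.

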7.2 Recording of Adverse Events

Whenever possible, a unifying diagnosis should be recorded in the eCRF as the AE rather than individual signs or symptoms. Similarly, the unifying diagnosis should be recorded as the AE rather than the abnormal laboratory result (i.e. "anemia" instead of "low hemoglobin").

If the AE is a worsening of a past medical condition, the AE should clearly indicate that the past medical condition has worsened using words such as "worsening," "aggravated," or "exacerbation."

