7.3.4 Treatment Required

Treatment required as a result of an AE will be recorded in the subject's source documents, and if medication is required, on the Concomitant medications log:

- None

- Medication Required (record on Concomitant Medications eCRF)
- Hospitalization Required
- Other (specify)

If a diagnosis has been entered as an AE, the treatment(s) recorded may represent the treatment(s) given for one or more sign(s) or symptoms(s) (e.g. Naproxen for the AE “fracture”, without recording “pain due to fracture” or “inflammation due to fracture” as separate AEs).

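### The pooled dysphagia rate can miss swallowing events recorded only as aspiration or coded as choking; consider a pre-specified broad row beside it

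*SAP*

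**What the plan says.** SAP 9.9.1 plans exposure-adjusted incidence rates that "will also be presented for the above TEAE overview categories, all preferred terms, and selected AEs of interest". They are shown in four columns: C-15 active, C-15 placebo, C-16 Rollover and C-16 Switch. The rate is "Number of patients with given event/ Person-years for the event", and a subject with the event contributes time only up to the first event of that type.

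The dysphagia group is "Dysphagia: Aphagia, Dysphagia". Fall is among the events taken by exact term: "AEs of agitation, somnolence, insomnia, anxiety and fall will be defined as events with matched preferred terms". Neither definition contains a choking, aspiration, fracture or injury term. In the same section Parkinsonism has 14 terms. Suicidality has 9, running from ideation to completed suicide.

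On recording, Protocol 7.2 says: "Whenever possible, a unifying diagnosis should be recorded in the eCRF as the AE rather than individual signs or symptoms". Adverse events are coded in MedDRA 16.1 (SAP 9.9.1).

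**The concern.** The term list and the recording rule do not fit together well. The list looks for the symptom, while the rule asks sites to prefer the diagnosis. Where a swallowing problem has led to aspiration and the site enters only that diagnosis, the subject has no matching term. Choking is outside the group whatever the recording rule says, simply because no choking term is listed.

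Swallowing is a risk that this study screens for and follows. An SDQ score of 11 or more excludes a subject (Protocol 4.3), the SDQ is scheduled at nearly every clinic visit, and a missing SDQ counts as a protocol deviation (SAP 9.6). The dysphagia row is the one place where the SAP pools swallowing adverse events into a single subject-level rate. A reader will take that row as the summary of the risk, so it should be as complete as a short term list can make it.

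**Working it through.** The plan gives no figure to reproduce: there is no assumed event rate, and the sample size has no statistical basis (Protocol 8.5, SAP 8.2). The check is a reading of the text, followed by an illustration resting on stated assumptions.

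**1. Which records the dysphagia row counts**

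| How the event reaches the database | Counted? |
|---|---|
| Dysphagia or Aphagia recorded, alone or with a consequence | Yes |
| Aspiration diagnosis recorded alone, as Protocol 7.2 permits | No |
| Event coded as choking, with no dysphagia term | No |
| Aspiration or choking after an earlier recorded dysphagia event | Subject already counted |

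**2. Direction within a column.** Let n subjects have a listed term and k have only a choking or aspiration term. The narrow count is n and the broad count is n + k. Person-years stop at the first qualifying event, so broad person-years cannot exceed narrow person-years. The narrow rate therefore cannot exceed the broad rate, and the proportional shortfall in the rate is at least k/(n + k). With k = 0 that floor is zero. The documents give neither n nor k.

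**3. Illustration (assumptions, not document figures).** Take a constant event rate, with a share s of events recorded only under an outside term. Then narrow rate = (1 − s) × broad rate.

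| Broad rate per person-year | s = 0 | s = 10% | s = 25% | s = 50% |
|---|---|---|---|---|
| 0.050 | 0.050 | 0.045 | 0.0375 | 0.025 |
| 0.100 | 0.100 | 0.090 | 0.075 | 0.050 |
| 0.150 | 0.150 | 0.135 | 0.1125 | 0.075 |

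With the planned numbers (about 36 Switch, 80 Rollover, 116 in all) and an assumed mean exposure of one year, one missed subject lowers the rate by about 1/36 = 0.028 (Switch), 1/80 = 0.013 (Rollover) or 1/116 = 0.009 (all) per person-year. At two years these halve: 1/72 = 0.014, 1/160 = 0.006 and 1/232 = 0.004.

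**4. Can the pooled figure be rebuilt from other tables?** Aspiration and choking terms get their own rates in the same four columns. Adding those rates to the dysphagia rate does not give the broad rate, for two reasons. A subject with two of the terms would be counted twice, and each rate stops its person-years at a different first event. The pooled rate needs a group defined at subject level.

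**5. Does the same reasoning reach falls?** The rule in Protocol 7.2 replaces signs and symptoms by a diagnosis. A fall is a cause of a fracture, not a sign or symptom of it. The fracture example in Protocol 7.3.4 begins "If a diagnosis has been entered as an AE, the treatment(s) recorded may represent" and ends "without recording “pain due to fracture” or “inflammation due to fracture” as separate AEs". It sets aside the pain and inflammation of a fracture and says nothing about leaving out the fall. The mechanism in step 1 therefore does not carry over.

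**The case against.** The strongest reply is that nothing is hidden. Exposure-adjusted rates for every preferred term appear in the same four columns, serious TEAEs are tabulated by system organ class and preferred term, all SAEs are listed, and the SDQ total score is summarised by visit with confidence intervals (SAP 9.9.1 and 9.9.7). This stands, and it is the main reason the point is minor. It does not supply a pooled subject-level rate, as step 4 shows, and SDQ means describe symptom scores, not clinical events.

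A second reply is that the recording rule applies only where possible, and that the protocol elsewhere treats complications as adverse events in their own right (Protocol 7.1.1 and 7.1.5). A site may well record both dysphagia and its consequence, and then the subject is counted. This also stands: the row can miss such subjects, but it need not.

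A third concerns falls. A reader might infer that a fall with a fracture is entered only as the fracture and so leaves the Fall rate. The documents do not support that, for the reason in step 5. Counting every fracture or injury as a fall would also bring in unrelated events, since Protocol 1.1 describes later chorea "with an increased risk of injury from falling or flailing into objects": flailing is a separate route to injury.

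**Conclusion.** The point holds for dysphagia, in limited form. The listed terms can miss a subject whose swallowing problem is recorded only as aspiration or coded as choking, and no other planned output gives the pooled rate that would include that subject. Within a column the narrow rate can only equal or fall below the broad one. The size is unknown: the percentages in the illustration follow from assumed values of s, and zero is possible.

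A reader might go further in two ways that the documents do not support. One is that the more serious the event, the less likely it is to be counted. That is plausible if serious events more often receive a diagnosis, but nothing in either document shows such a gradient. The other is that the comparison with Study C-15 is biased. The same term list applies to all four columns and the C-15 recording rule is not given, so neither the presence nor the direction of such a bias can be stated.

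The point is worth considering as a cheap improvement to a descriptive safety table. It does not threaten the study's conclusions.

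**What to change.** In SAP 9.9.1, keep the narrow dysphagia row and add a broad one: Aphagia and Dysphagia plus the preferred terms for choking, aspiration and aspiration pneumonia. Take exact names from MedDRA 16.1 and fix the list before the tables are run; if it is added later, SAP 8.4 would have it identified as unplanned. Show the broad rate with the serious events in it for C-15 active, C-15 placebo, Rollover and Switch.

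The cost is one short term list and one table row. The downside is that some aspiration or choking events not due to dysphagia will be included, which is why the narrow row stays.

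For falls, leave the definition as it is. At most, add a supportive row for fractures and injuries attributed to a fall by medical review of the existing adverse event records, with the reviewer blinded to cohort. That review is the only appreciable extra work, and it is optional.
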